4.2.1. Choice of Contraception/Barrier Requirements

Human reproductive safety data are limited for nirmatrelvir/ritonavir, but there is no suspicion of human teratogenicity based on the intended pharmacology of the compound. Therefore, the use of a highly effective method of contraception is required for female participants who are not pregnant on study entry (see [Appendix 4](#)).

4.2.2. Collection of Retained Research Samples

Retained Research Samples will be collected and stored for further analyses which may, for example, provide greater understanding of the study intervention.

4.2.3. Inclusion of Pediatric Participants

This study includes participants of 12 years of age and older and weighing ≥ 40 kg, which is consistent with the Fact Sheet for nirmatrelvir/ritonavir where FDA has granted EUA for the treatment of mild-to-moderate COVID-19 in adults and pediatric patients (12 years of age and older and weighing ≥ 40 kg)[[16](#)].

4.3. Justification for Dose

On 22 December 2021, the US FDA granted EUA to nirmatrelvir/ritonavir for the treatment of mild-to-moderate COVID-19 in adults and pediatric patients (12 years of age or older weighing at least 40 kg) who are at risk for progression to severe disease. The recommended dose is 300 mg nirmatrelvir co-administered with 100 mg ritonavir q12h for 5 days for subjects with normal renal function or mild renal impairment. This dose was well tolerated in Study C4671005 and reduced the rate of hospitalization or death by 89% compared with placebo in symptomatic adult participants with COVID-19 who were at increased risk of progression to severe disease.

Results from the renal impairment study showed that the adjusted geometric mean (90% CI) test/reference ratios comparing moderate renal impairment (test) to normal renal function (reference) for nirmatrelvir AUC_{inf} and C_{max} was 187.40% (148.52%, 236.46) and 138.12% (113.18%, 168.55%), respectively. Due to the increase in exposures of nirmatrelvir in those with moderate renal impairment, and verified by modeling and simulation, the nirmatrelvir/ritonavir dose in patients with moderate renal impairment was reduced to 150 mg/100 mg q12h.

4.4. End of Study Definition

The end of the study is defined as the date of the last visit of the last participant in the study.

A participant is considered to have completed the study if they have completed all periods of the study, including the last visit.

5. STUDY POPULATION

This study can fulfill its objectives only if appropriate participants are enrolled, including participants across diverse and representative racial and ethnic backgrounds. If a prescreening tool is utilized for study recruitment purposes, it will include collection of information that reflects the enrollment of a diverse participant population including, where permitted under local regulations, age, sex, race, and ethnicity. The following eligibility criteria are designed to select participants for whom participation in the study is considered appropriate. All relevant medical and nonmedical conditions should be taken into consideration when deciding whether a particular participant is suitable for this protocol.

Prospective approval of protocol deviations to recruitment and enrollment criteria, also known as protocol waivers or exemptions, is not permitted.

5.1. Inclusion Criteria

Participants are eligible to be included in the study only if all of the following criteria apply:

Age and Sex:

1. Participants aged 12 years or older and weighing ≥ 40 kg at screening ([Section 10.10.1](#)).
 - Refer to [Appendix 4](#) for reproductive criteria for female ([Section 10.4.1](#)) participants.

Disease Characteristics:

2. Participants must have written documentation with patient-reported 100% compliance (ie, completed a 5 day course of nirmatrelvir/ritonavir). They must have symptom alleviation or resolution in COVID-19 signs/symptoms followed by a worsening (rebound) of signs/symptoms after completing an initial 5-day course of nirmatrelvir/ritonavir based on the judgement of both the participant and investigator ([Section 10.10.2](#)).
3. The onset of rebound in COVID-19 symptoms must occur within 2 weeks (14 days) after the completion of the initial 5-day course of nirmatrelvir/ritonavir.
4. Onset of rebound in signs/symptoms attributable to COVID-19 within 48 hours prior to randomization and ≥ 1 sign/symptom attributable to COVID-19 present on the day of randomization ([Section 10.10.2](#)).
5. SARS-CoV-2 infection as determined by rapid antigen testing in any specimen collected within 24 hours prior to randomization and collected within 2 weeks (14 days) after the completion of the initial 5-day treatment course of nirmatrelvir/ritonavir.
6. Has at least 1 characteristic or underlying medical condition associated with an increased risk of developing severe illness from COVID-19 ([Section 10.10.4](#)).

5.2. Exclusion Criteria

Participants are excluded from the study if any of the following criteria apply:

Medical Conditions:

1. Current need for hospitalization, hospitalized for the index COVID-19 infection, or anticipated need for hospitalization within 24 h after randomization in the clinical opinion of the site investigator.
2. History of severe chronic liver disease (eg, jaundice, ascites, hepatic encephalopathy, history of bleeding esophageal or gastric varices). No laboratory testing is needed.
3. History of hypersensitivity or other contraindication to any of the components of the study interventions, as determined by the investigator.
4. Suspected or confirmed concurrent active systemic infection other than COVID-19 that may interfere with the evaluation of response to the study intervention.
5. Receiving dialysis or eGFR <30 mL/min/1.73 m² (for adults) or eCrCl <30 mL/min (for adolescents) at screening using creatinine point of care device (see [Section 10.7.1](#) for age-specific kidney function calculation).
6. Oxygen saturation of <92% on room air obtained at rest within 24 hours prior to randomization ([Section 10.10.4](#)).
7. Immunocompromised ([Section 10.10.7](#)).
8. Other medical or psychiatric condition including recent (within the past year) or active suicidal ideation/behavior or laboratory abnormality that may increase the risk of study participation or, in the investigator's judgment, make the participant inappropriate for the study.

Prior/Concomitant Therapy:

9. Current use of any prohibited concomitant medication(s) (see [Section 6.9](#); [Appendix 8](#), and [Section 10.10.6](#)).
10. COVID-19 vaccination within 14 days prior to study entry or anticipated COVID-19 vaccination through Day 34.
11. Receiving other COVID-19 specific treatments within 30 days of randomization and through Day 34, excluding a single 5-day treatment course of nirmatrelvir/ritonavir as well as blinded study medication ([Section 10.10.6](#)).

Prior/Concurrent Clinical Study Experience:

12. Prior participation in this trial.

13. Current or previous administration with an investigational product (drug or vaccine) within 30 days (or as determined by the local requirement) or 5 half-lives preceding the first dose of study intervention used in this study (whichever is longer).

Other Exclusion Criteria:

14. Females who are pregnant up to 14 weeks gestation. Pregnancy \geq 14 weeks is not exclusionary.
15. Investigator site staff directly involved in the conduct of the study and their family members, site staff otherwise supervised by the investigator, and sponsor and sponsor delegate employees directly involved in the conduct of the study and their family members.

5.3. Lifestyle Considerations

5.3.1. Contraception

All female participants who are not pregnant at study entry, and who in the opinion of the investigator, are biologically capable of having children must agree to use a highly effective method of contraception consistently and correctly for at least 28 days after the last study intervention.

Note: If the childbearing potential changes after start of the study (eg, a premenarchal female participant experiences menarche) or the risk of pregnancy changes (eg, a female participant who was not heterosexually active becomes active), the participant must discuss this with the investigator, who should determine if a female participant must begin a highly effective method of contraception. If reproductive status is questionable, additional evaluation should be considered.

The investigator or their designee, in consultation with the participant, will confirm that the participant is utilizing an appropriate method of contraception for the individual participant and their partner(s) from the permitted list of contraception methods (see [Section 10.4.3](#)) and will confirm that the participant has been instructed in its consistent and correct use. At time points indicated in the [SoA](#), the investigator or designee will inform the participant of the need to use highly effective contraception consistently and correctly and document the conversation and the participant's affirmation in the participant's chart. Participants need to affirm their consistent and correct use of at least 1 of the selected methods of contraception, considering that their risk for pregnancy may have changed since the last visit.

In addition, the investigator or designee will instruct the participant to call immediately if the selected contraception method is discontinued and document the requirement to use an alternate protocol-specified method, including if the participant will no longer use abstinence as the selected contraception method, or if pregnancy is known or suspected in the participant or partner.

5.4. Screen Failures

Screen failures are defined as participants who consent to participate in the clinical study but are not subsequently enrolled in the study. A minimal set of screen failure information is required to ensure transparent reporting of screen failure participants to meet the CONSORT publishing requirements and to respond to queries from regulatory authorities. Minimal information includes demography, screen failure details, and any SAE.

Individuals who do not meet the criteria for participation in this study (screen failure) may not be rescreened.

To assist in further understanding rebound, the following screen failure information will be captured in the eCRF and included in the study report.

- Number (%) of participants with rebound symptoms at time of screening but who are negative by rapid antigen testing at screening and therefore screen fail for the study.

5.5. Criteria for Temporarily Delaying Enrollment/Randomization/Administration of Study Intervention

Not applicable.

6. STUDY INTERVENTION(S) AND CONCOMITANT THERAPY

Study interventions are all prespecified investigational and noninvestigational medicinal products/auxiliary medicinal products, medical devices, and other interventions (eg, surgical and behavioral) intended to be administered to the study participants during the study conduct.

For the purposes of this protocol, study intervention refers to nirmatrelvir 150 mg tablets and matching placebo and ritonavir 100 mg capsules.

6.1. Study Intervention(s) Administered

Study intervention will be self-administered by the participant OR administered to the participant by a legal guardian or caregiver.

A legal guardian or caregiver may administer study medication. Study personnel should review dose administration requirements with the participant, and, as appropriate, with the delegated caregiver(s) (may include school nurse) before administration and throughout the study as necessary.

Study Intervention(s)			
Intervention Name	Nirmatrelvir	Placebo for nirmatrelvir	Ritonavir
Arm Name (group of participants receiving a specific	nirmatrelvir/ritonavir	placebo	ritonavir

Study Intervention(s)			
treatment or no treatment)			
Type	drug	placebo	drug
Dose Formulation	tablet	tablet	capsule
Unit Dose Strength(s)	150 mg	0 mg	100 mg
Dosage Level(s)	300 mg q12h for 5 days 150 mg q12h for 5 days (for participants with eGFR \geq 30 to $<$ 60 mL/min/1.73 m ² (or eCrCl \geq 30 to $<$ 60 mL/min) at screening)	0 mg q12h for 5 days	100 mg q12h for 5 days
Route of Administration	Oral	Oral	Oral
Use	Experimental	Placebo	Experimental
IMP or NIMP/AxMP	IMP	IMP	IMP
Sourcing	Provided centrally by the sponsor. Refer to the IPM.	Provided centrally by the sponsor. Refer to the IPM.	Provided centrally by the sponsor. Refer to the IPM.
Packaging and Labeling	Study intervention will be provided in blister wallets. Each wallet will be labeled as required per country requirement. Products will be provided with blinded labels.	Study intervention will be provided in blister wallets. Each wallet will be labeled as required per country requirement. Products will be provided with blinded labels.	Study intervention will be provided in HDPE bottles. Each bottle will be labeled as required per country requirement. Products will be provided with open labels.
Current/Former Name(s) or Alias(es)	PF-07321332	NA	ritonavir

Study Arm(s)		
Arm Title	Nirmatrelvir/ritonavir	Placebo/ritonavir
Arm Type	Experimental	Other
Arm Description	Participants will receive nirmatrelvir/ritonavir 300 mg/100 mg (or 150 mg/100 mg for participants with	Participants will receive placebo 0 mg/ritonavir 100 mg q12h for 5 days.

	eGFR \geq 30 to $<$ 60 mL/min/1.73 m 2 or eCrCl \geq 30 to $<$ 60 mL/min) q12h from Day 1 through Day 5.	
Associated Intervention Labels	Nirmatrelvir/ritonavir	Placebo/ritonavir

6.1.1. Administration

The first dose of study intervention will be administered at the site.

Nirmatrelvir 150 mg tablets or placebo for nirmatrelvir will be administered with ritonavir 100 mg for 5 days. Participants will be dispensed 1 blister wallet card of nirmatrelvir 150 mg tablets and 1 bottle of ritonavir capsules at the Day 1 site visit. Participants will be instructed to take:

- 2 tablets of nirmatrelvir 150 mg or placebo for nirmatrelvir q12h;
- 1 capsule of ritonavir 100 mg q12h.
 - Participants with moderate renal impairment (eGFR \geq 30 to $<$ 60 mL/min/1.73 m 2 [or eCrCl \geq 30 to $<$ 60 mL/min] at screening) will receive either 1 tablet of nirmatrelvir 150 mg and placebo for nirmatrelvir or 2 tablets of placebo for nirmatrelvir. The dose for ritonavir remains unchanged (ie, participants will receive 1 capsule of ritonavir 100 mg q12h).

Participants should take the first dose of study intervention on Day 1, during the in-person visit; that is, participants should take nirmatrelvir/placebo and ritonavir at the same time (no more than 15 minutes apart). The study intervention should be taken every 12 hours (\pm 4 hours), and not more than twice in a calendar day. Depending on the time of first dose, the timing of the second dose may be adjusted slightly to allow the participant/caregiver to select a convenient 12 hour dosing schedule as long as the next dose is taken at least 4 hours, but no later than 16 hours, after the first dose. Once the dosing schedule is adjusted, all subsequent doses should be taken every 12 hours (\pm 4 hours).

If a dose is delayed, it should be taken as soon as possible (but no later than 8 hours after the scheduled 12-hourly dose time), then resume the normal dosing schedule. If the participant misses a dose by more than 8 hours, the participant should not take the missed dose and instead take the next dose at the regularly scheduled time. The participant should not double the dose to make up for a missed dose. Dosing should be stopped at the end of the treatment period (Day 5 or 6). Any remaining tablets and/or capsules at the Day 5 visit should be returned. If the Day 5 visit is conducted prior to the last dose of study intervention (ie. Day 6), any remaining tablets or capsules should be collected at the next visit.

Participants will swallow the study intervention whole and will not manipulate or chew the study intervention prior to swallowing. Participants may take the study intervention with or without food. Taking study intervention with food may improve tolerability. Refer to the IPM for additional dosing and administration instructions.

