6.8. Treatment of Overdose

Study sites should warn parents/caregivers to store the study intervention out of reach of children and to provide close supervision when intervention will be self-administered by the child.

For this study, any dose of nirmatrelvir greater than 900 mg (or any dose greater than 450 mg for participants on the reduced nirmatrelvir dose for moderate renal impairment) or ritonavir greater than 300 mg within a 24-hour time period will be considered an overdose.

There is no specific treatment for an overdose.

In the event of an overdose, the investigator should:

1. Contact the study medical monitor within 24 hours.

Closely monitor the participant for any AEs/SAEs and laboratory abnormalities as medically appropriate and at least until the next scheduled follow-up.

2. Document the quantity of the excess dose as well as the duration of the overdose in the CRF.
3. Overdose is reportable to Pfizer Safety **only when associated with an SAE**.

Decisions regarding dose interruptions or modifications will be made by the investigator in consultation with the study medical monitor as needed based on the clinical evaluation of the participant.

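### The dosing-time clauses in Protocol Section 6.1.1 conflict with each other and, on one reading of ±4 hours, permit dosing that Section 6.8 defines as an overdose

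*Protocol*

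**What the plan says.** Protocol Section 6.1.1 contains four timing rules.

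- General interval and daily limit: every 12 hours, plus or minus 4, "and not more than twice in a calendar day".
- Second dose: its time may be adjusted to reach a convenient schedule, "as long as the next dose is taken at least 4 hours, but no later than 16 hours, after the first dose". After that, "all subsequent doses should be taken every 12 hours", again with the ±4 hours.
- Delayed dose: take it as soon as possible, "but no later than 8 hours after the scheduled 12-hourly dose time), then resume the normal dosing schedule".
- Missed dose: beyond 8 hours late, skip it and wait for the next regular time.

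The amount per dose is in the same section: "2 tablets of nirmatrelvir 150 mg or placebo for nirmatrelvir q12h" with one 100 mg ritonavir capsule. Participants with moderate renal impairment "will receive either 1 tablet of nirmatrelvir 150 mg and placebo for nirmatrelvir or 2 tablets of placebo for nirmatrelvir", with ritonavir unchanged.

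Section 6.8 sets overdose thresholds of more than 900 mg nirmatrelvir, or more than 450 mg on the reduced dose. For the other component, "ritonavir greater than 300 mg within a 24-hour time period will be considered an overdose".

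**The concern.** A participant with one late evening dose may find that the delayed-dose rule and the calendar-day limit give opposite answers. A participant who uses the second-dose flexibility may, depending on what ±4 hours means, take enough within a day to meet the overdose definition while keeping to Section 6.1.1.

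At stake are safety oversight and consistent classification. Under Section 6.8 an overdose calls for contact with the medical monitor within 24 hours, close monitoring and CRF documentation. Section 6.5 makes any departure from protocol-specified dosing a protocol deviation. Section 8.4.10 counts administration at the wrong time among medication errors and asks for sponsor notification of a dosing error within 24 hours. Where the clauses disagree, two sites could record the same dose times as compliant, a deviation or an overdose. The SAP would not expose this, because its compliance measure (Section 6.5.3) is doses received over doses planned and takes no account of spacing.

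**Working it through.** **Inputs.** From Protocol 6.1.1: first interval 4 to 16 h; later doses every 12 ± 4 h; at most two doses per calendar day; delay allowance up to 8 h. Per dose: nirmatrelvir 2 × 150 = 300 mg (150 mg on the reduced dose) and ritonavir 100 mg. From Protocol 6.8: thresholds of 900, 450 and 300 mg in 24 h.

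**Step 1: the thresholds expressed in doses.** 900/300 = 450/150 = 300/100 = 3. The limits are consistent with each other. Three doses in 24 h are not an overdose, and a fourth is.

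**Step 2: delayed dose against the calendar-day limit.** Take an 08:00/20:00 schedule. The 20:00 dose is taken at 02:00, which is 6 h late and within the 8 h allowed. The schedule resumes at its regular times, 08:00 and 20:00. The calendar day then holds 02:00, 08:00 and 20:00: three doses against a limit of two. On this schedule, any evening dose 4 to 8 h late falls between 00:00 and 04:00 and has the same result. This step does not depend on how ±4 h is read.

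**Step 3: delayed dose against 12 ± 4 h.** A dose taken d hours late leaves 12 − d hours to the next scheduled dose. At d = 8 that is 4 h, while 12 ± 4 gives a minimum of 8 h. The remaining gap is below 8 h for every d above 4. Read instead as a window around a clock time, a delay of up to 8 h lies outside ±4 h. The section does not say that the delay rule is an exception.

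**Step 4: four doses, with ±4 h as the interval between successive doses.** The shortest intervals are 4, 8 and 8 h, so the fourth dose comes at 4 + 8 + 8 = 20 h. Example: 12:00 and 16:00 on Day 1, 00:00 and 08:00 on Day 2, two per calendar day. A half-hour grid search with the calendar-day limit imposed gave these shortest spans from first to fourth dose:

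| First dose at | Shortest span |
|---|---|
| 08:00 | 24 h |
| 09:00 | 23 h |
| 10:00 | 22 h |
| 11:00 | 21 h |
| 12:00 to 19:30 | 20 h |
| 20:00 | 28 h |

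Before noon the calendar-day limit holds the third dose back to midnight. From 20:00 a second dose 4 h later already falls on Day 2, which pushes the fourth dose to Day 3. In between, the limit prevents nothing.

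Totals for four doses:
- nirmatrelvir 4 × 300 = 1200 mg against 900 mg;
- reduced dose 4 × 150 = 600 mg against 450 mg;
- ritonavir 4 × 100 = 400 mg against 300 mg, in both arms.

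Each total is 4/3 of its threshold.

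**Step 5: four doses, with ±4 h as a window around a fixed schedule set by the second dose.** Dose 2 at 4 h puts dose 3 at 16 ± 4 h (earliest 12 h) and dose 4 at 28 ± 4 h (earliest 24 h). The span is at least 24 h, on the edge of the period in 6.8.

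**Step 6: where the short span comes from.** Four doses with no interval under 8 h span at least 3 × 8 = 24 h. An interval shorter than 8 h is therefore needed to bring the span below 24 h, and Section 6.1.1 provides one at the second dose.

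**The case against.** The section repeatedly speaks of a schedule and of regular times, which favours the fixed-window reading. On that reading the fourth dose reaches only the 24-hour boundary. This stands, so a reader should not infer without qualification that a compliant participant can meet the overdose definition. That follows only if ±4 hours is an interval between doses, and the text supports either reading.

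The 20-hour sequence is also a corner case. Dose 2 comes 8 hours early under a clause meant for slight adjustment, and doses 3 and 4 are each taken at the shortest interval. Ordinary use, such as 16:00, 20:00, 08:00 and 20:00, puts dose 4 at 28 hours. This stands too. A reader might infer that every participant is affected because both arms take ritonavir. All are subject to the rules, but only someone dosing near each limit would reach the thresholds.

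The delayed-dose conflict does not lead to an overdose: 02:00, 08:00 and 20:00 total 900 mg and 300 mg, which equal the limits without exceeding them. That is correct, and it limits the conflict to Section 6.1.1.

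The delay rule and the 4-hour second dose can be read as exceptions to the general interval. That is reasonable for the interval, although the section does not say so. It does not remove the clash with the calendar-day limit, for which no exception is hinted at, and it does not reconcile the second-dose rule with Section 6.8.

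A reader might also infer that reported overdose counts or trial results would be distorted. The SAP plans no analysis of overdose counts, Section 6.8 makes overdose reportable to the sponsor's safety group only with an SAE, and no endpoint or estimand depends on dose spacing.

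Finally, Section 6.1.1 refers to the investigational product manual for further dosing instructions. It is not among the documents, so what participants are actually told cannot be judged here.

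**Conclusion.** The concern holds in two parts of different strength. The conflict within Section 6.1.1 is firm: a dose carried past midnight under the delay rule, with the schedule then resumed at its regular times, breaks the calendar-day limit on any reading of ±4 hours. The 8-hour allowance also fits 12 ± 4 hours only as an unstated exception.

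The conflict with Section 6.8 is conditional. It gives four doses in 20 hours, one third above every threshold, if ±4 hours is the interval between doses and the first dose falls from noon to before 20:00. For first doses after 08:00 and before noon the span is longer but still under 24 hours. It shrinks to a boundary case if ±4 hours is a window around a fixed schedule.

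The sequence is probably uncommon and the efficacy analysis is not touched. The point is still worth acting on, because it concerns stated safety rules and how sites classify dosing events.

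**What to change.** The sponsor should reconcile the clauses of Section 6.1.1 (second-dose flexibility, ±4 hours, the delayed-dose rule and the calendar-day limit) with each other and with the 24-hour thresholds in Section 6.8. The text should state which reading of ±4 hours applies, and the participant instructions should be aligned with it. The rule and its values are for the sponsor's clinical team; none is proposed here.

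The cost is a short wording change in the protocol and participant materials, with the ethics review that an amendment needs. No visits or procedures are added. The amendment history (Section 10.12) records that dose timing was aligned with related protocols, so the sponsor should check whether the same wording appears there.
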